5.8.6 Patient Reported Outcomes (PROs)

Patient self-reported measures will be assessed using selected PROMIS domains for gastrointestinal symptoms, physical function, and satisfaction with participation in social roles, described in APPENDIX E. These instruments will be scored according to the recommendation of the developers. For each PROMIS domain, scores at baseline and at Day 28, 90, and 180

post-randomization will be described by treatment arm using descriptive statistics. Wilcoxon signed rank tests will be used to evaluate changes from baseline to each follow-up time point for each arm. Wilcoxon rank sum tests will compare the changes between arms at each of these time points.

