4.3.2 Assessments

Assessment and/or reporting of the following is required for participants enrolled on this study. All assessments are considered standard-of-care unless identified below by “*”. Assessments indicated by “**” are for research purposes.

Prior to Enrollment

The following pre-enrollment assessments must be completed prior to enrolling the participant in the EDC system and within the designated timeframe listed below.

1. Complete aGVHD staging and grading information including assessments of rash, diarrhea, nausea/vomiting, and bilirubin, within 24 - 72 hours prior to enrollment. Biopsy results of involved tissue, if performed as SoC, should also be reported.
2. Medical history within 24 – 72 hours prior to enrollment.

3. Albumin and CK level within 24 – 72 hours prior to enrollment.
4. Complete blood count (CBC) with differential and platelet count within 24 - 72 hours prior to enrollment.
5. Renal function (blood urea and/or blood urea nitrogen, creatinine) within 24 - 72 hours prior to enrollment.
6. Schistocytes, haptoglobin and LDH within 24 - 72 hours prior to enrollment.
7. Pregnancy test (urine or serum) for females of child-bearing potential within 30 days prior to enrollment.
8. Recording of Concomitant medications starting at 7 days prior to randomization

Baseline Assessments

Baseline assessments listed below must be completed at time of enrollment and prior to the first dose of study therapy unless otherwise specified.

1. Physical exam including height and weight, participant disease/transplantation baseline variables
2. Karnofsky Performance Status (may be completed pre- or post-enrollment)
3. Baseline patient-reported outcome measures (see APPENDIX E)
4. Peripheral blood for EBV and CMV viral load (within 72 hours prior to first dose of study drug)
5. CBC with differential and platelet count
6. Recording and review of Concomitant medications
 - a. For all immunosuppressant agents, the overall start and stop date will be captured. For agents where dosing is tapered in response to drug levels, the medication dosing will not require reporting.
 - b. Dosing for corticosteroids will be captured for all dosing changes.
7. Peripheral blood* for Peripheral Blood Mononuclear Cells (PBMC) testing (See APPENDIX B)
8. Peripheral blood* for Flow Cytometry and Immune Profiling (See APPENDIX B)
9. Peripheral blood* for humoral response (ADA) testing for T-Guard arm only(See APPENDIX B)

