5.1.2 Randomization and Blinding

Participants will be randomized at the time of enrollment in a 1:1 ratio to the treatment arms. Randomization will be stratified by center region (US vs. Europe) and age group (at least 55 years vs. under 55). Stratified treatment assignments will be generated using permuted blocks of random sizes.

As this is an open-label trial, no blinding will be performed.

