5.6.8 GVHD-free Survival

GVHD-free survival is defined as being alive, in CR, and free of cGVHD. The proportion of participants with GVHD-free survival at Days 90 and 180 post-randomization will be estimated for each treatment arm using sample proportions and 95% Wilson score or Clopper-Pearson CIs, as appropriate. The proportions of participants with GVHD-free survival at Day 180 will be compared between arms using logistic regression with adjustment for the stratification factors and for acute GVHD grade at randomization (Grade III vs. IV).

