5.8.4 Evolution of Cell Populations

The evolution of specific cell populations over the 180-day follow-up period will be evaluated using samples obtained from approximately 50 participants (25 T-Guard and 25 ruxolitinib participants) at Days 0, 14, 28, 90 and 180 post-randomization. Specimens will either be collected and stored as viably frozen PBMCs to allow for phenotypic and functional analysis of specific cell subsets or collected in CytoChex blood preservation tubes for FCM analysis.

The following cell populations, amongst others, will be measured by flow cytometry analysis: Inflammatory Monocytes & Dendritic Cells, Recent Thymic Emigrants, CD4+, CD8+ Naïve & Memory Cells, CD4+ T Regulatory Cells, NK Cells, $\gamma\delta$ T Cells, and B cells.

The level of each cell population will be summarized for each arm using descriptive statistics at each assessment time considered. Changes in levels from baseline to each follow-up assessment time will be evaluated by arm using Wilcoxon signed rank tests. For the PBMC subsets collected from both arms, Wilcoxon rank sum tests will compare the changes between arms at each follow-up time point.

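### Patient-reported outcomes are compared between arms by unadjusted rank-sum tests on change from baseline, so precision available from the collected baseline score is left unused

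*Combined protocol and SAP*

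**What the plan says.** Section 5.8.6 summarizes PROMIS domain "scores at baseline and at Day 28, 90, and 180" by arm, tests within-arm change with signed-rank tests, and then states that "Wilcoxon rank sum tests will compare the changes between arms at each of these time points". It names no covariate and specifies no between-arm estimate or confidence interval. Section 5.8.4 handles the cell populations in the same way, in about 25 participants per arm: "For the PBMC subsets collected from both arms, Wilcoxon rank sum tests will compare the changes between arms at each follow-up time point".

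The information needed for adjustment is collected. Section 4.3.2 requires the baseline questionnaire at enrollment and before the first dose. Section 5.1.2 says that "Randomization will be stratified by center region (US vs. Europe) and age group". Grade at randomization (III vs. IV) is a covariate in the primary model (5.5) and in most of the model-based secondary comparisons, for example 5.6.4 and 5.6.6 to 5.6.10. Section 5.1.5 itself says, about the primary endpoint, that adjusting for the stratification factors raises power over an unadjusted comparison.

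Patient-reported outcomes and cell populations are exploratory (2.3.3). No power, effect size, SD, correlation or significance level is given for either.

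**The concern.** Baseline adjustment usually helps most when the outcome itself is measured at baseline, which is the case here. A change score fixes the baseline coefficient at 1. When the correlation between visits is moderate and the SDs are similar, that subtracts too much and adds baseline noise to the comparison.

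A chance baseline imbalance also passes into the result. With equal SDs, correlation rho and a baseline difference of delta between arms, the expected difference in change is the treatment effect minus (1 - rho) x delta.

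At stake is the precision of the plan's only patient-reported comparison between a short infusion course and continuing oral treatment, in a sample already reduced by early deaths.

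**Working it through.** The plan states no power or effect for patient-reported outcomes, so there is no figure to reproduce.

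**Inputs from the documents**
- Planned size: 246 randomized 1:1, so 123 per arm (5.1.5, 5.1.2).
- Expected Day 30 mortality of 15-20% (5.3.2): 123 x 0.85 = 105 and 123 x 0.80 = 98. About 100 per arm is used for Day 28.
- Expected Day 60 mortality of 40% (5.3.2): 123 x 0.60 = 74. About 75 per arm is used for later visits. This is optimistic, because it assumes no further deaths and complete questionnaires.

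**Assumed, because the documents are silent**
- Two-sided 5% test.
- Effect of 0.4 follow-up SD.
- Correlation rho of 0.5, with 0.3 to 0.7 shown.
- Equal SDs at baseline and follow-up, relaxed below.

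**Formulas** (follow-up SD = 1)
- Variance of the change score: 2(1 - rho).
- Variance after baseline adjustment: 1 - rho².
- Ratio: 2/(1 + rho), which is above 1 for every rho below 1.
- Power = Phi(d / sqrt(2v/n) - 1.96).

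**Worked example** (n = 100 per arm, rho = 0.5)
- Change: v = 1.00; 0.4/sqrt(0.0200) = 2.83; Phi(0.87) = 80.7%.
- Adjusted: v = 0.75; 0.4/sqrt(0.0150) = 3.27; Phi(1.31) = 90.4%.

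| n per arm | rho | Change score | Baseline-adjusted | Gain (points) |
|---|---|---|---|---|
| 100 | 0.3 | 66.7% | 84.3% | 17.6 |
| 100 | 0.5 | 80.7% | 90.4% | 9.7 |
| 100 | 0.7 | 95.5% | 97.7% | 2.3 |
| 75 | 0.5 | 68.8% | 80.7% | 12.0 |

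Gains are taken before rounding.

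**Relaxing the equal-SD assumption.** Let k be the baseline SD divided by the follow-up SD. The change-score variance is then 1 + k² - 2 rho k, which exceeds the adjusted variance by (k - rho)². At n = 100 and rho = 0.5:
- k = 0.7: variance 0.79, power 88.9% against 90.4%, a gain of 1.5 points.
- k = 0.5: variance 0.75, no gain.
- k = 1.2: variance 1.24, power 71.9% against 90.4%, a larger gain.

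**Checking the actual rank test.** The formulas use normal-theory means, whereas the plan uses a rank-sum test. Simulating normal data at n = 100 and 0.4 SD (3,000 runs per setting), rank-sum on change had about 65%, 79% and 94% power at rho 0.3, 0.5 and 0.7. ANCOVA had about 84%, 89% and 98%, and rank ANCOVA about 81%, 87% and 96%. The pattern holds.

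The further gain from region, age group and grade cannot be computed, because their association with the scores is not given.

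**The case against.** The strongest reply is that nothing here is wrong. The rank-sum test is valid under randomization, the objective is to describe changes, and no power is promised. The plan is also tiered: most secondary comparisons use adjusted models, while exploratory ones use simple tests (Barnard's in 5.8.1, Gray's in 5.8.2, 5.8.3 and 5.8.7). All of this stands and keeps the point minor. It does not remove a gain in precision that needs no new data.

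A reader might infer that the plan loses about 10 points of power. The documents do not support that. The figure needs a correlation near 0.5, equal SDs and starting power near 80%, none of which is stated. Eligibility limited to Grade III-IV disease could plausibly narrow the baseline spread and shrink the gain, although the documents give no data on this.

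A reader might also carry the figures over to the cell populations. That is not supported either. About 25 per arm is too few for four covariates beside the arm term, cell counts are probably skewed, and a rank-sum test can be more efficient than ANCOVA on raw skewed values.

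Nor is adjustment free of drawbacks. ANCOVA adds a modelling assumption. A rank ANCOVA gives a test and not a difference in score units. In the simulation with 25 per arm and rho 0.9, rank ANCOVA did about 4 points worse than rank-sum on change (81% against 85%).

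Baseline questionnaires may be completed after allocation is known, since treatment can start up to 72 hours after randomization in an open-label trial. That affects the change score as much as the adjusted analysis.

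**Conclusion.** The point holds as a minor improvement for patient-reported outcomes. The planned test is valid but leaves out baseline and stratification information that the trial collects. For a 0.4 SD effect, about 100 per arm and equal SDs, the gain in power is about 10 points at a correlation of 0.5, 18 at 0.3 and 2 at 0.7. It is about 1.5 points if the baseline SD is 0.7 of the follow-up SD with correlation 0.5. No power figure is claimed for the cell populations.

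It should not be read as a fix for mortality. Day 90 and Day 180 changes exist only for survivors, section 5.8.6 gives no rule for deaths, and adjustment does not supply one.

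**What to change.** In section 5.8.6, make the between-arm comparison at each visit an ANCOVA of the follow-up score on arm, baseline score, region, age group and aGVHD grade at randomization. Report the adjusted difference with its 95% CI. Keep either the planned rank-sum test or a rank-based ANCOVA (as a test only) as a robustness check, and keep the within-arm signed-rank summaries.

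In section 5.8.4, adjust at most for the baseline value alone, on a rank or log scale.

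The cost is SAP wording, settled before any comparison by arm is seen; no new data are needed. The drawbacks are the linear-model assumption and a possible slight loss in very small samples at high correlation.

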5.8.7 Thrombotic Microangiopathy (TMA)

The frequency of TMA events will be tabulated for each treatment arm. The cumulative incidence of TMA will be described by arm using the Aalen-Johansen estimator, with death treated as a competing risk. Estimates and 95% CIs of the cumulative incidence of TMA will be provided at Day 28 post-randomization. The cumulative incidence of TMA will be compared between arms using Gray's test.

5.8.8 EASIX Score

EASIX score at enrollment will be summarized by treatment arm using descriptive statistics. The proportion of participants with high EASIX OS risk (defined as an EASIX score greater than 3.43) and high EASIX NRM risk (EASIX score greater than 3.61) at the time of enrollment will also be described for each arm, the risk classifications proposed in Luft et al. 2017.

Validation of these EASIX risk categories will be performed in the context of SR-aGVHD treatment considered in the current trial. OS and NRM at Day 180 post-randomization will be estimated for each EASIX risk group (high vs. not) by treatment arm using the Kaplan-Meier and Aalen-Johansen estimators, respectively. A Cox proportional hazards model will evaluate the prognostic value of EASIX OS risk (high vs. not) on the hazard rate of overall mortality while adjusting for treatment arm and a EASIX risk-treatment arm interaction term to permit possible differential effects of the treatments based on EASIX classification. A similar Cox model of the cause-specific hazard rate of NRM will evaluate the prognostic value of EASIX NRM risk (high vs. not) while adjusting for treatment arm and a EASIX risk-treatment arm interaction term.

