5 STATISTICAL CONSIDERATIONS

5.1 STUDY DESIGN AND OBJECTIVE

This trial is a randomized, open-label, multi-center Phase 3 study designed to compare the efficacy and safety of T-Guard to ruxolitinib treatment of participants with Grade III-IV SR-aGVHD. A total of 246 participants will be enrolled from approximately 75 transplant centers in the US and Europe. All participants will be followed at minimum through Day 180 post-randomization.

The study will begin with a safety run-in phase of 24 randomized participants (12 to each arm), after which the remaining participants will be enrolled provided that safety concerns do not arise during the run-in.

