5.8 ANALYSIS OF EXPLORATORY ENDPOINTS

The analysis of exploratory endpoints will be based on the ITT analysis population.

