5.8.5 GVHD-related Biomarkers

Using the biomarker risk model from Major-Monfried, Renteria et al. 2018, the serum levels of GVHD-related biomarkers including REG3 α and ST2 and the 3-IS urine levels at enrollment and Day 6, 14, and 28 post-randomization will be used to estimate NRM probabilities for each participant at Day 180 following each assessment time point. The proportions of participants with high risk (defined as an estimated NRM greater than 0.29) will be described at each assessment time by treatment arm.

Moreover, the proportions of participants within each treatment arm experiencing a Day 28 CR will be described separately for participants with high risk vs. not at enrollment within each treatment arm using sample proportions and 95% Wilson score or Clopper-Pearson CIs, as appropriate. A logistic regression model will evaluate the prognostic value of biomarker risk (high vs. not) on the chance of attaining a Day 28 CR while adjusting for treatment arm.

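### Section 5.8.8 does not say which contrast of its EASIX-by-arm interaction model expresses prognostic value; the EASIX coefficient alone, under 0/1 arm coding, would describe one arm only

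*Combined protocol and SAP*

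**What the plan says.** Section 5.8.8 classifies participants as high risk or not (for mortality, "defined as an EASIX score greater than 3.43") and sets out to validate these categories in the trial's setting. It plans Kaplan-Meier and Aalen-Johansen estimates at Day 180 for each EASIX group by arm, and then two regressions. For mortality: "A Cox proportional hazards model will evaluate the prognostic value of EASIX OS risk (high vs. not) on the hazard rate of overall mortality". The same sentence then puts both arm and the product term into that model: "while adjusting for treatment arm and a EASIX risk-treatment arm interaction term to permit possible differential effects of the treatments". For NRM: "A similar Cox model of the cause-specific hazard rate of NRM will evaluate the prognostic value of EASIX NRM risk (high vs. not"), again with arm and the interaction.

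The section does not state the arm coding, the reference arm, the coefficient or contrast that carries the conclusion, or a significance level. It gives no assumed hazard ratio, share of high-risk participants or power.

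Section 5.8.5 puts a similar question about the biomarkers: "A logistic regression model will evaluate the prognostic value of biomarker risk (high vs. not) on the chance of attaining a Day 28 CR". That model adjusts for treatment arm and has no interaction term.

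**The concern.** Once a model contains a product term, there is no EASIX main effect that is independent of how arm is coded. The wording presents the EASIX term as the answer and the interaction as an adjustment. An analyst who follows it literally, with software that uses 0/1 coding, would report the reference-arm effect as the prognostic value of EASIX in the trial. Another analyst with the other arm as reference would fit the same model and report a different estimate and p-value. Both would have followed the plan.

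The stated purpose of the interaction, to allow treatment effects to differ by EASIX class, is a question of effect modification. It is a legitimate question, but not the same as whether EASIX predicts death. At stake is how clearly an exploratory validation can be interpreted.

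**Working it through.** **What the coefficient means.** Let E = 1 for high EASIX and A = 0/1 for arm:

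log h(t) = log h0(t) + b1·E + b2·A + b3·E·A

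- EASIX log hazard ratio in the arm coded 0: b1.
- In the arm coded 1: b1 + b3.
- If the coding is reversed, the coefficient on E becomes b1 + b3.
- With arm coded -1/2 and +1/2, the coefficient on E is b1 + b3/2, the average over arms.

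The first, third and fourth readings come from the same fitted model and the same likelihood. None of this needs an assumed effect size.

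**Inputs from the documents.**
- Section 5.1: "A total of 246 participants will be enrolled from approximately 75 transplant centers in the US and Europe". Allocation is 1:1 (Section 5.1.2), so 123 per arm. Section 5.8: "The analysis of exploratory endpoints will be based on the ITT analysis population".
- Section 1.3.1.2.4 gives 6-month survival of 60% for pooled T-Guard data and 48.7% for REACH2. Applied to all 246, these give 246 × 0.40 = 98 and 246 × 0.513 = 126 deaths. Applied by arm, 123 × 0.40 + 123 × 0.513 = 112. A 45% mortality gives 246 × 0.45 = 111. Using these rates for a Grade III-IV population is itself an assumption. Section 5.3.2 already expects 40% mortality by Day 60, so deaths could be more numerous.

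**Inputs assumed, because the documents give none.** Two-sided 5% test; 20-50% with high EASIX; hazard ratio 1.3-3.0; the same EASIX effect in both arms. The plan states no power for this analysis, so there is no figure to reproduce.

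**Power by the Schoenfeld formula.** With D deaths and share p at high risk, power = Φ(|log HR|·√(D·p·(1-p)) - 1.96). The main-effects model uses D; the reference-arm coefficient uses about D/2.

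Example with D = 112, p = 0.30, HR 1.75 (log HR 0.560):
- EASIX and arm only: √(112 × 0.21) = 4.850; 0.560 × 4.850 - 1.96 = 0.75; power 77.5%.
- Reference-arm coefficient: √(56 × 0.21) = 3.429; 0.560 × 3.429 - 1.96 = -0.04; power 48.4%.

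| High EASIX | HR | EASIX + arm | Reference-arm coefficient | Loss (points) | 2-df joint test |
|---|---|---|---|---|---|
| 30% | 1.5 | 50.3% | 28.5% | 21.8 | 40.3% |
| 30% | 1.75 | 77.5% | 48.4% | 29.1 | 67.9% |
| 30% | 2.0 | 91.9% | 66.2% | 25.8 | 86.2% |
| 50% | 1.5 | 57.4% | 32.9% | 24.5 | 47.0% |
| 50% | 1.75 | 84.2% | 55.3% | 28.8 | 75.9% |
| 50% | 2.0 | 95.6% | 73.7% | 21.9 | 91.8% |

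Losses are taken from unrounded values. Over the full grid (98, 112 or 126 deaths, 20-50% high EASIX, HR 1.3-3.0) the loss runs from 0.8 to 29.2 points. The 2-df joint test of EASIX and its interaction loses at most about 10.5.

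**The arm-averaged contrast.** Each arm-specific log hazard ratio has variance of about 2/(D·p·(1-p)). Their mean has variance ¼ × 2 × 2/(D·p·(1-p)) = 1/(D·p·(1-p)), the same as in the main-effects model. The planned model can therefore answer the prognostic question almost without loss.

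**Simulation check.** 1,500 Cox fits per scenario; 246 participants, 30% high EASIX, 45% Day 180 mortality, no true interaction:

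| HR | EASIX + arm | Reference-arm coefficient | 2-df joint | Arm-averaged contrast |
|---|---|---|---|---|
| 1.75 | 81.3% | 53.5% | 72.0% | 79.8% |
| 2.0 | 94.0% | 70.9% | 88.6% | 93.6% |

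A separate simulation with about 111 deaths made EASIX matter only in the non-reference arm. The lone EASIX coefficient then rejected in about 5% of trials, its null rate.

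**The case against.** The strongest reply is that the plan never says the lone EASIX coefficient will be tested. Arm-specific hazard ratios, a joint test, effect coding and an arm-averaged contrast all fit the text. That is correct. A reader might infer from 5.8.8 that EASIX is tested in one arm only, or that half the deaths are discarded, but the documents do not support either. The fitted model uses every death; only one possible reading of it does not.

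The interaction is also deliberate. If EASIX does act differently in the two arms, a main-effects hazard ratio is only an average, and the power comparison above assumes no such difference, which favours the simpler model. This stands, and is why the interaction should be kept.

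Sections 5.8.5 and 5.8.8 model different outcomes and need not match. The comparison shows only that the plan has a simpler form for a prognostic question.

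Finally, an EASIX effect confined to one arm would be visible in the planned estimates by EASIX group and arm, and in the interaction term. That is so, but those estimates do not settle which number is reported as prognostic value.

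**Conclusion.** The point holds as an unspecified contrast with a poor default reading. That the coefficient depends on coding is algebra. The power loss is conditional: about 20-30 points if the coefficient is read under 0/1 coding, with a two-sided 5% test, 30-50% high EASIX, a hazard ratio of 1.5-2.0, about 111 deaths and no true interaction. A reader might take that as a fixed cost of the planned model. It is not: over wider assumptions the loss is about 1-29 points, and with an arm-averaged contrast it is 1.5 points or less in every scenario simulated. The figures are for overall mortality; the documents give no event count for NRM.

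Nor do the documents support saying that a validation would fail, because they set no pass/fail rule. The related objective (Section 2.3.3) is only to describe the score at screening. The analysis is exploratory, with no power target, and no primary or key secondary conclusion depends on it. This is a low-priority improvement.

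**What to change.** In Section 5.8.8, for overall mortality and for cause-specific NRM:

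1. Estimate and test prognostic value in a Cox model with EASIX risk and treatment arm only, as Section 5.8.5 does for the biomarkers. Alternatively, name the arm-averaged EASIX contrast from the interaction model. Report the hazard ratio with its 95% CI.
2. Keep the EASIX-by-arm interaction in a second model, test it separately, and report the EASIX hazard ratio with 95% CI within each arm.

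The cost is a sentence or two in the plan and no new data. The small downside is that the main-effects hazard ratio is an average if the arms truly differ; the second model would show that.
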